5.3.2.3. Prior and concomitant medications

Incomplete prior/concomitant medication dates will be imputed as follows:

- If the medication date is missing completely, then the medication date will be replaced by the start of study treatment.
- If the day of medication date is missing, but the month and year are equal to the start of study treatment, then the medication date will be replaced by the start of study treatment. For example, if the medication start date is --/JAN/2015, and study treatment start date is 15/JAN/2015, then the imputed medication start date will be 15/JAN/2015.
- If both the day and month of medication start date are missing but the start year is equal to the start of study treatment, then the medication date will be replaced by the start of study treatment. For example, if the medication start date is --/--/2014, and study treatment start date is 19/NOV/2014, then the imputed medication start date will be 19/NOV/2014.
- In all other cases the missing medication day or missing medication month will be replaced by 1.
- Incomplete stop date will be replaced by the last day of the month (if day is missing only), if not resulting in a date later than the date of patient's death. In the latter case the date of death will be used to impute the incomplete stop date.
- In all other cases the incomplete medication stop date will not be imputed.

5.3.2.4. Exposure

No imputation will be done for first dose date. Date of last dose of study drug if unknown or partially unknown will be imputed as follows:

- If the last date of study drug is completely missing and there is no End of Treatment eCRF page and no death date, the patient should be considered to be ongoing and use the cut-off date for the analysis as the last dosing date

- If the last date of study drug is completely or partially missing and there is EITHER an End of Treatment eCRF page OR a death date available (within the cut-off date), then imputed last dose date is:
 - = 31DECYYYY, if only Year is available and Year < Year of min (EOT date, death date)
 - = Last day of the month, if both Year and Month are available and Year = Year of min (EOT date, death date) and Month < the month of min (EOT date, death date)
 - = min (EOT date, death date), for all other cases.

5.3.3. Imputation Rules for Date of Last Contact and Efficacy Assessments

5.3.3.1. Date of Last Contact

The date of last contact will be derived for patients not known to have died at the analysis cut-off using the latest complete date among the following:

- All patient assessment dates (blood draws (laboratory, PK), vital signs, performance status, ECG, disease assessments)
- Start and end dates of anti-cancer therapies administered after study treatment discontinuation
- AE start and end dates
- Last date of contact collected on the 'Survival Follow-up' eCRF (do not use date of survival follow-up assessment unless status is 'alive')
- Study drug start and end dates
- Randomization date
- Withdrawal of consent date
- Date of discontinuation on disposition eCRF pages (do not use if reason for discontinuation is lost to follow-up).

Only dates associated with actual examinations of the patient will be used in the derivation. Dates associated with a technical operation unrelated to patient status such as the date a blood sample was processed will not be used. Assessment dates after the cut-off date will not be applied to derive the last contact date.

5.3.3.2. Date of Death

Missing or partial death dates will be imputed based on the last contact date:

- If the date is missing, it will be imputed as the day after the date of last contact
- If the day or both day and month is missing, death will be imputed to the maximum of the full (non-imputed) day after the date of last contact and the following:
 - Missing day: 1st day of the month and year of death;
 - Missing day and month: January 1st of the year of death.

5.3.3.3. Tumor Assessments

All investigation dates (e.g., PET/CT scan, CT scan) must be completed with day, month and year.

If there are multiple scan dates associated with an evaluation, i.e., radiological assessments occur over a series of days rather than the same day, the choice of date of assessment could impact the date of progression and/or date of response. If there are multiple scan dates associated with an evaluation, the earliest of the scan dates associated with the evaluation will be used as the date of assessment.

If one or more investigation dates for an evaluation are incomplete but other investigation dates are available, the incomplete date(s) are not considered for calculation of the assessment date and assessment date is calculated as the earliest of all investigation dates.

If all measurement dates for an evaluation have no day recorded, the 1st of the month is used. If the month is not completed, for any of the investigations for an evaluation, the missing month will be imputed with the planned month for the assessment between the previous and the following assessment. If both a previous and following assessments are not available, this assessment will not be used for any calculations.

5.3.3.4. Date of Start of New Anticancer Therapy

Incomplete dates for start date of new anti-cancer therapy (drug therapy, radiation, surgery) will be imputed as follows and will be used for determining censoring dates for efficacy analyses and in the derivation of the end of on-treatment period. PD date below refers to PD date by investigator assessment.

- The end date of new anti-cancer therapy will be included in the imputations for start date of new anti-cancer therapy. If the end date of new anti-cancer therapy is
 - completely missing then it will be ignored in the imputations below
 - partially missing with only year (YYYY) available then the imputations below will consider 31DECYYYY as the end date of the new anti-cancer therapy

- partially missing with only month and year available then the imputations below will consider the last day of the month for MMMYYYY as the end date of the new anti-cancer therapy
- For patients who have not discontinued study treatment at the analysis cut-off date, last dose of study treatment is set to the analysis cut-off date in the imputations below.
- If the start date of new anti-cancer therapy is completely or partially missing then the imputed start date of new anti-cancer therapy is derived as follows:
 - Start date of new anti-cancer therapy is completely missing

Imputed start date = min [max(PD date + 1, last dose of study treatment + 1), end date of new anti-cancer therapy]
 - Only year (YYYY) for start of anti-cancer therapy is available

IF YYYY < Year of min [max(PD date + 1, last dose of study treatment + 1), end date of new anti-cancer therapy] THEN imputed start date = 31DECYYYY;

ELSE IF YYYY = Year of min [max(PD date + 1, last dose of study treatment + 1), end date of new anti-cancer therapy]

THEN imputed start date = min [max(PD date + 1, last dose of study treatment + 1), end date of new anti-cancer therapy]

ELSE IF YYYY > Year of min [max(PD date + 1, last dose of study treatment + 1), end date of new anti-cancer therapy]

THEN imputed start date = 01JANYYYY
- Both Year (YYYY) and Month (MMM) for start of anti-cancer therapy are available
 - IF YYYY = Year of min [max(PD date + 1, last dose of study treatment + 1), end date of new anti-cancer therapy], AND

MMM < Month of min [max(PD date + 1 day, last dose of study treatment + 1 day), end date of new anti-cancer therapy]

THEN imputed start date = DAY (Last day of MMM) MMM YYYY;
 - ELSE IF YYYY = Year of min [max(PD date + 1, last dose of study treatment + 1), end date of new anti-cancer therapy], AND

MMM = Month of min [max(PD date + 1 day, last dose of study treatment + 1 day), end date of new anti-cancer therapy]

THEN imputed start date = min [max(PD date + 1 day, last dose of study treatment + 1 day), end date of new anti-cancer therapy]);

- ELSE IF YYYY = Year of min [max(PD date + 1, last dose of study treatment + 1), end date of new anti-cancer therapy], AND

 MMM > Month of min [max(PD date + 1 day, last dose of study treatment + 1 day), end date of new anti-cancer therapy]

 THEN imputed start date = 01 MMM YYYY;

- ELSE IF YYYY < Year of min [max(PD date + 1, last dose of study treatment + 1), end date of new anti-cancer therapy]

 THEN imputed start date = DAY (Last day of MMM) MMM YYYY;

- ELSE IF YYYY > Year of min [max(PD date + 1, last dose of study treatment + 1), end date of new anti-cancer therapy]

 THEN imputed start date = 01 MMM YYYY.

6. ANALYSES AND SUMMARIES

Refer to Section 4 for definitions of analysis sets and Section 5.2 for general methodology.

All summaries will be by treatment group using the data from Phase 1b and Phase 2 separately.

6.1. Primary Endpoints

6.1.1. DLT for Phase 1b

6.1.1.1. Main Analysis

- Estimand strategy: All DLT data from DLT-evaluable participants during the DLT observation period (28 days following C1D1) will be included in the analysis.
- Analysis set: DLT Evaluable Set.
- Intercurrent events and missing data: The data from participants who are not DLT-evaluable will be excluded. Participants without DLTs who stopped treatment before receiving at least 80% of the planned dose of PF-07901801 and at least 75% of the planned dose of any component of the tafasitamab and lenalidomide regimen will be excluded. No imputations for missing data will be performed.
- Analysis methodology: DLTs will be listed and summarized by treatment group. DLT rate will be calculated for each treatment group as the number of DLT-evaluable

participants with DLTs in the DLT observation period divided by the number of DLT-evaluable participants.

6.1.2. OR as assessed by the Investigator per Lugano 2014 response criteria for Phase 2

6.1.2.1. Main Analysis

- Estimand strategy: All OR data from Phase 2 will be included in the analysis.
- Analysis set: Safety Analysis Set.
- Intercurrent events and missing data: All data collected after an intercurrent event of subsequent anticancer therapy will be excluded. Participants who do not have a post-baseline disease assessment due to early PD, who receive anticancer therapies other than the study treatment prior to achieving an objective response, or who die, experience PD, or stop disease assessments for any reason prior to achieving an objective response will be counted as non-responders. Missing data will be imputed following Section 5.3.
- Analysis methodology: Assessment of response will be made as per investigator using Lugano 2014 response criteria. The analyses will be by treatment group.

Best overall response (BOR) will be assessed based on reported overall responses at different evaluation time points from the 'start date' until documented disease progression, according to the following rules. Only tumor assessments performed before the start of any further anti-cancer therapies will be considered in the assessment of BOR.

CR = at least 1 determination of CR before first documentation of progression

PR = at least 1 determination of PR before first documentation of progression (and not qualifying for a CR)

SD = at least 1 SD assessment \geq 6 weeks after the 'start date' and before first documentation of progression (and not qualifying for CR or PR).

PD = at least 1 PD assessment (and not qualifying for CR, PR or SD).

Not Evaluable (NE): all other cases.

Objective response (OR) is defined as BOR of CR or PR according to Lugano 2014 response criteria.

Patients who do not have an on-treatment tumor assessment due to early progression, who receive anti-tumor therapies other than the study treatments prior to reaching a CR or PR, or who die, progress, or drop out for any reason prior to reaching a CR or PR will be counted as non-responders in the assessment of OR. Each patient will have an objective response status (0: no OR; 1: OR). OR rate (ORR) is the proportion of patients with OR in the analysis set.

ORR by treatment group will be calculated along with the 2-sided 95% CI using the Wilson method (with continuity correction).

In addition, the frequency (number and percentage) of patients with a BOR of CR, PR, SD, PD and NE will be tabulated. Patients with BOR of NE will be summarized by reason for having NE status. The following reasons will be used:

- No adequate baseline assessment
- No post-baseline assessments due to death
- No post-baseline assessments due to other reasons
- All post-baseline assessments have overall response NE
- New anti-cancer therapy started before first post-baseline assessment
- SD of insufficient duration (< 6 weeks after 'start date')

6.2. Secondary Endpoints

Refer to Section [6.7](#) for safety endpoints.

The following analyses will be based on the Safety Analysis Set.

In addition to what is described below, the objective response (OR) will also be analyzed similar to that described in Section [6.1.2.1](#) for Phase 1b in the Safety Analysis Set.

6.2.1. Complete Response

CR is defined as a BOR of CR per Lugano Response Classification Criteria 2014 as assessed by the investigator, from the 'start date' until the first documentation of PD, death or start of new anti-cancer therapy. CR rate (CRR) is defined as the proportion of participants with a CR.

Point estimate of CRR will be calculated along with corresponding 2-sided 95% CI using the Wilson method (with continuity correction).

6.2.2. Duration of Response

Duration of response (DoR) is defined, for participants with an OR per Lugano Response Classification Criteria 2014, as the time from the first documentation of objective response (CR or PR) to the date of first documentation of PD or death due to any cause.

If a patient has not had an event (PD or death), DoR is censored at the date of last adequate tumor assessment. The censoring rules for DoR are as described in [Table 4](#).

DoR (months) = [date of event or censoring – first date of OR +1]/30.4375

Table 4 Outcome and Event Dates for DoR Analyses

Scenario	Date of event/censoring	Outcome
PD or death - After at most one missing or inadequate post-baseline tumor assessment, OR - ≤ 22 weeks after 'start date'	Date of PD or death	Event
PD or death - After 2 or more missing or inadequate post-baseline tumor assessments	Date of last adequate tumor assessment ^a documenting no PD before new anti-cancer therapy is given or missed tumor assessments	Censored
No PD and no death	Date of last adequate tumor assessment ^a documenting no PD before new anti-cancer therapy is given or missed tumor assessments	Censored
Treatment discontinuation due to 'Disease progression' without documented progression	Not applicable	Information is ignored. Outcome is derived based on documented progression only.
New anti-cancer therapy given	Date of last adequate tumor assessment ^a documenting no PD before new anti-cancer therapy is given or missed tumor assessments	Censored

^a If there are no adequate post-baseline assessments prior to PD or death, then the time without adequate assessment should be measured from the 'start date'; if the criteria were met the censoring will be on the 'start date'.

Kaplan-Meier estimates (product-limit estimates) will be presented by treatment group together with a summary of associated statistics including the median DoR time with 2-sided 95% CIs. In particular, the DoR rate at 3, 6, 9 and 12 months (and in subsequent 6-month increments as appropriate) will be estimated with corresponding 2-sided 95% CIs. The CIs for the median will be calculated according to Brookmeyer and Crowley (1982)^[3] and the CIs for the survival function estimates at the time points defined above will be derived using the log-log transformation according to Kalbfleisch and Prentice (2002)^[4] (conftype=loglog default option in SAS Proc LIFETEST) with back transformation to a CI on the untransformed scale. The estimate of the standard error will be computed using Greenwood's formula.

Depending on the number of ORs, DoR may be displayed graphically and analyzed using Kaplan-Meier methodology. If the number of patients with OR is small, the Kaplan-Meier method may not provide reliable estimates. In this case, only descriptive statistics or listings will be provided.

Frequency (number and percentage) of patients with each event type (PD or death) and censoring reasons will be presented by treatment group. Reasons for censoring will be summarized according to the categories in Table 5 following the hierarchy shown.

Table 5 DoR Censoring Reasons and Hierarchy

Hierarchy	Condition	Censoring Reason
1	Start of new anti-cancer therapy	Start of new anti-cancer therapy
2	Event after 2 or more missing or inadequate post-baseline tumor assessments/ 'start date'	Event after 2 or more missing assessments ^a
3	No event and [withdrawal of consent date \geq 'start date' OR Follow Up Discontinuation Reason = 'withdrawal by subject']	Withdrawal of consent
4	No event and lost to follow-up in any disposition page	Lost to follow-up
5	No event and [EOS present OR disposition page for any epoch after screening says patient will not continue into any subsequent phase of the study] and no adequate post-baseline tumor assessment	No adequate post-baseline tumor assessment
6	No event and none of the conditions in the prior hierarchy are met	Ongoing without an event

^a 2 or more missing or inadequate post-baseline tumor assessments.

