###### **Duration of Response**

DoR is defined, for participants with an objective response per Lugano Response Classification Criteria 2014, as the time from the first documentation of objective response until PD, or death due to any cause, whichever occurs first.

DoR will be censored on the date of the last adequate disease assessment for participants who do not have an event (PD or death due to any cause), on the date of the last adequate disease assessment before the new anti-cancer therapy for participants who start a new anti-cancer therapy prior to an event, or on the date of the last adequate disease assessment before the 2 or more missing disease assessments for participants with an event after 2 or more missing disease assessments.

DoR will be summarized using Kaplan Meier method and displayed graphically. Median DoR and 2-sided 95% CI (based on the Brookmeyer-Crowley method) will be provided.

DoR will be summarized by dose levels for Phase 1b and Phase 2 of the study separately.

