5.2.12. Analyses for Continuous and Qualitative Variables

Continuous variables will be summarized using descriptive statistics ie, number of nonmissing values and number of missing values [ie, n (missing)], mean, median, standard deviation, minimum, maximum and first and third quartile (Q1 and Q3).

Qualitative variables will be summarized by frequency counts and percentages. Unless otherwise specified, the calculation of proportions will include the missing category. Therefore, counts of missing observations will be included in the denominator and presented as a separate category.

In case the analysis refers only to certain visits, percentages will be based on the number of participants still present in the study at that visit, unless otherwise specified.

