6.2.3. Duration of Complete Response

Duration of complete response (DoCR) is defined, for participants with a CR per Lugano Response Classification Criteria 2014, as the time from the first documentation of a CR until PD, or death due to any cause, whichever occurs first.

DoCR (months) = [date of event or censoring – first date of CR +1]/30.4375

DoCR will be analyzed in the same way as that is for DoR as described in Section 6.2.2.

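### SAP 6.2.2 lets summary statistics or listings replace Kaplan-Meier for DoR and DoCR when responders are few, with no threshold and no rule for censored durations

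*SAP*

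**What the plan says.** The default in SAP 6.2.2 is clear: "Kaplan-Meier estimates (product-limit estimates) will be presented by treatment group together with a summary of associated statistics including the median DoR time", with a Brookmeyer-Crowley interval for the median. The section then adds an exception: "If the number of patients with OR is small, the Kaplan-Meier method may not provide reliable estimates". What follows from it is: "In this case, only descriptive statistics or listings will be provided". No responder count triggers the switch, and the choice between the two options is left open.

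Three other SAP passages bear on what the exception would produce.

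- SAP 6.2.2 defines the variable for every responder, censored or not: "DoR (months) = [date of event or censoring – first date of OR +1]/30.4375".
- SAP 5.2.12 holds the SAP's general definition: "Continuous variables will be summarized using descriptive statistics ie" counts of non-missing and missing values and then "mean, median, standard deviation, minimum, maximum and first and third quartile (Q1 and Q3"). SAP 5.2.13, the separate section for time-to-event endpoints, specifies Kaplan-Meier.
- SAP 6.2.3 extends the rule: "DoCR will be analyzed in the same way as that is for DoR as described in Section 6.2.2".

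SAP 6.2.2 also tabulates event types and reasons for censoring by treatment group. That table does not depend on whether Kaplan-Meier is used.

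Protocol 9.4.3.1 has no exception for small numbers: "DoR will be summarized using Kaplan Meier method and displayed graphically", by dose level, with the median and its 95% CI. It specifies the same method for DoCR. SAP 2.1, which records modifications to the protocol's analysis plan, is marked not applicable.

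**The concern.** A censored duration is a lower bound on the true one. Kaplan-Meier uses it as such. A plain mean, median or quartile of the DoR variable treats it as complete. If the descriptive-statistics option is taken as SAP 5.2.12 defines it, a method that respects censoring gives way to one that does not, and the reported figure partly measures length of follow-up.

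The exception may well be the rule in practice. Phase 2 will not start, so only Phase 1b remains: about 20 participants over three planned dose levels, each reported separately. With no threshold in an open-label study, the choice between Kaplan-Meier and the fallback can also be made after the durations have been seen. PFS (SAP 6.2.4) is reported for the same small groups and has no such exception.

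**Working it through.** The passage states no figure to reproduce. The check has three parts.

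**1. How many responders per dose level?** Protocol 4.1 and 9.6 require at least 2 to 4 DLT-evaluable participants at each level and about 6 to 9 at the MTD or highest safe level. As a gauge only, take the 60% ORR that Protocol section 2 quotes for tafasitamab plus lenalidomide.

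| Participants at the level | Expected responders (n × 0.60) | Chance of 5 or fewer |
|---|---|---|
| 2 | 1.2 | 100% |
| 4 | 2.4 | 100% |
| 6 | 3.6 | 1 − 0.6^6 = 95% |
| 9 | 5.4 | 52% |

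On any ordinary meaning of few, most levels would qualify.

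**2. A small example.** Take five responders with durations 2, 4+, 8, 10+ and 11+ months, where + marks censoring.

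- Pooled summary: median 8.0; mean (2 + 4 + 8 + 10 + 11)/5 = 7.0; SD 3.9.
- Kaplan-Meier: S = 4/5 = 0.80 after month 2. At month 8 three are at risk, so S = 0.80 × 2/3 = 0.533. The curve never falls to 0.5, so the median is not reached.

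The pooled summary reports 8 months where the data show only that the median has not been reached.

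**3. Size of the possible bias.** The documents give neither a DoR distribution nor the follow-up of responders, so these are assumptions: 4 responders; exponential DoR with true median M of 6, 12 or 24 months; censoring times uniform on (a, b) = (3, 15) or (6, 18) months. With λ = ln 2/M:

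- expected censored fraction = (e^(−λa) − e^(−λb)) / (λ(b − a));
- expected pooled mean = (1 − censored fraction)/λ;
- average pooled median, by simulation of min(DoR, censoring time).

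For M = 12 and (3, 15): λ = 0.0578, censored fraction = (0.841 − 0.420)/0.693 = 0.61, and pooled mean = 0.393 × 17.3 = 6.8 months.

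| True median (mean) | Censoring window | Censored | Pooled mean | Average pooled median | Pooled median too low by |
|---|---|---|---|---|---|
| 6 (8.7) | 3–15 | 38% | 5.3 | 5.0 | 16% |
| 6 (8.7) | 6–18 | 27% | 6.3 | 6.0 | 0% |
| 12 (17.3) | 3–15 | 61% | 6.8 | 6.7 | 44% |
| 12 (17.3) | 6–18 | 51% | 8.5 | 8.4 | 30% |
| 24 (34.6) | 3–15 | 77% | 7.8 | 7.7 | 68% |
| 24 (34.6) | 6–18 | 71% | 10.0 | 10.1 | 58% |

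The pooled mean is too low in every row. The pooled median is close to the truth only where follow-up is long relative to DoR. A listing that flags censored values pools nothing, so none of this applies to it.

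**The case against.** A reader might infer that the SAP treats censored durations as finished ones, and that DoR will therefore be understated. The documents do not say that. Listings are an equal option. SAP 5.2.12 is written for continuous variables, and nothing ties it to DoR, which belongs to the time-to-event endpoints of SAP 5.2.13. The censoring-reason table, with a category for responses ongoing without an event, would show how many durations are incomplete. All of this stands, so the bias is conditional. The counts, however, do not correct a pooled mean or median printed beside them.

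A reader might also infer that later-opened, higher dose levels will look less durable because they have been followed for less time. The documents do not support this. They give no follow-up by level, and Protocol 4.3.3 allows later participants to be backfilled into lower levels already found safe, which can narrow or reverse any difference. Nor do they show how many responses will be censored. Protocol 4.1 runs Phase 1b to the last participant's last visit, although Protocol 10.1.10 allows non-safety assessments to stop earlier.

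The SAP's caution about Kaplan-Meier also has substance. With 4 responders and a true median of 12 months, the Kaplan-Meier median is not reached in about 42% or 29% of simulated trials under the two censoring windows. When it is reached, it averages about 6.0 or 6.8 months, no nearer to 12 than the pooled median. Part of that is selection, since short durations are the ones that bring the curve down to 0.5. So Kaplan-Meier is no cure for few responders. Its advantage is that it can report a median as not reached, which a pooled summary cannot.

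Finally, Protocol section 9 lets the SAP modify the planned analyses and requires an amendment only for major changes to the primary endpoints. DoR and DoCR are secondary, so the departure is permitted; what is missing is its record in SAP 2.1.

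**Conclusion.** The point holds as a gap in the fallback rule. SAP 6.2.2, and 6.2.3 by reference, has no responder threshold and no rule for censored durations. One of its two options, read with the SAP's own general definition and the DoR formula, pools censored with completed durations and can understate DoR. The understatement of the median runs from about 0% to 68% under the stated assumptions (4 responders, exponential DoR, uniform censoring), and it is governed by follow-up relative to DoR. Under the other option it is nil. These are secondary, descriptive endpoints in a study without hypothesis testing, so the consequence is a potentially misleading summary of durability; no test or decision rule depends on it. The remedy is cheap enough to be worth making.

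**What to change.** Reword the fallback in SAP 6.2.2; 6.2.3 then follows. Suggested text: *When responders are few, individual DoR and DoCR values will be listed or shown in a swimmer plot with censored values flagged (+), together with the numbers of events and censorings. Any median will be the Kaplan-Meier median, reported as not reached where that is so. No mean, SD, median or quartiles that pool censored with completed durations will be produced.*

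If a fallback from Kaplan-Meier is kept, state the number of responders below which it applies and record the departure from Protocol 9.4.3.1 in SAP 2.1.

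The cost is a few sentences and no new data. The drawback is that many medians or upper confidence limits will read as not reached or not estimable, which is a fair account of what so few responders can show.
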